GpCRC

Gastroparesis Clinical Research Consortium

Gastroparesis Registry (GpR)

Protocol

Confidential

1 December 2009

Gastroparesis Registry Protocol

Contents

De	sign synopsis 1	l
1.	Background and rationale31.1.Historical background1.2.Gastroparesis Clinical Research Consortium1.3.Mission of the GpCRC and overall objectives1.4.Gastroparesis Registry	3 3 3 1 4
2.	Objectives and hypotheses 5 2.1. Hypotheses to be tested 5	5 5
3.	Scientific background73.1.Clinical symptoms73.2.Epidemiology and natural history83.3.Pathogenesis and pathophysiology93.4.Diagnostic tests123.5.Treatment143.6.Management of refractory gastroparesis16	7739245
4.	Case definitions174.1.Gastroparesis174.2.Patients without nausea but with other symptoms suggestive of gastroparesis with delayed gastric emptying184.3.Symptomatic nausea and vomiting without delayed gastric emptying184.4.Target composition18	77333
5.	Screening and enrollment195.1.Inclusion criteria195.2.Exclusion criteria19	}
6.	Schedule of visits and procedures216.1.Screening visits216.2.Follow-up visits236.3.Data form contents236.4.Plasma, serum, and DNA for banking24	l 1 3 4
7.	Statistical and design considerations	5
8.	Human subjects issues	7

Contents

	8.1. 8.2. 8.3. 8.4.	Confidentiality	27 28 29 29
9.	Referen	ices	30
10.	Append	lix	34
	10.1.	Participating centers	35
	10.2.	Data collection schedule	36
	10.3.	Whole blood draw schedule	37
	10.4.	Glossary	38
	10.5.	Document history	39

Design synopsis

Objectives

- To establish a registry of patients with gastroparesis for the study of the epidemiology, etiology, and degree of morbidity associated with gastroparesis.
- To prospectively and systematically follow a well-characterized cohort to define the natural history and clinical course of gastroparesis.
- To provide a reliable resource for rapid recruitment of well-characterized patients with gastroparesis for therapeutic clinical trials, pathophysiological, molecular, histopathologic, or other ancillary studies. These subsequent clinical trials or other ancillary studies will each be conducted under separate study protocols with separate consent processes.

Type of study

• Observational

Population

- Patients at least 18 years of age
- Gastroparesis patients with delayed gastric emptying
- Patients without nausea, but with other symptoms suggestive of gastroparesis and with delayed gastric emptying
- Patients with symptomatic nausea and vomiting, but without delayed gastric emptying

Inclusion criteria

- Symptoms of gastroparesis of at least 12 weeks duration (do not have to be contiguous) with varying degrees of nausea, vomiting, abdominal pain, early satiety, postprandial fullness
- Completion of a 4-hour scintigraphic low fat Egg Beaters gastric emptying study
 - Patients with either or both abnormal 2 hour (>60% retention) and 4 hour (>10% retention) gastric emptying will be enrolled and classified as definite gastroparesis
 - Patients with normal gastric emptying, but with symptoms of gastroparesis may be enrolled and classified as possible gastroparesis
- Age at least 18 years at initial screening visit
- Ability and willingness to participate in follow-up

Exclusion criteria

- Inability to comply with or complete the gastric emptying test by scintigraphy
- Presence of other conditions that could explain the patient's symptoms:
 - Pyloric or intestinal obstruction
 - Active inflammatory bowel disease
 - Eosinophilic gastroenteritis
 - Neurological conditions such as increased intracranial pressure, space occupying or inflammatory/infectious lesions
 - Acute liver failure
 - Advanced liver disease
 - Acute renal failure
 - Untreated chronic renal failure (serum creatinine >3 mg/dL)
- Total or subtotal gastric resection (patients with prior fundoplication or postvagotomy

gastroparesis after pyloroplasty or antrectomy with Billroth I, Billroth II, or Roux-en-Y gastrojejunostomy will be eligible for enrollment)

- Any other plausible structural or metabolic cause
- Any other condition, which in the opinion of the investigator would interfere with study requirements
- Inability to obtain informed consent

Study duration

- Recruitment: Up to 700 patients until 31 March 2010
- Follow-up: 48-192 weeks (1-4 years)

Visit schedule

- Screening/entry into Gastroparesis Registry: enrollment must occur within 16 weeks of initiation of screening
- Follow-up visits at 16 weeks, 32 weeks, 48 weeks, 64 weeks, 80 weeks, 96 weeks, 112 weeks, 128 weeks, 144 weeks, 160 weeks, 176 weeks, and 192 weeks

Outcome measures

- Patient Assessment of Upper Gastrointestinal Disorders Symptom Severity Index (PAGI-SYM)
- Patient Assessment of Upper Gastrointestinal Disorders Quality of Life (PAGI-QOL)
- Scintigraphic gastric emptying test
- HbA1c and glucose levels
- Body mass index
- Health related quality of life (SF-36)
- Brief pain inventory
- Nutritional intake
- Investigator Derived Independent Outcome Measure Scores (IDIOMS)
- Management of gastroparesis
- Beck Depression Inventory
- State Trait Anxiety Inventory
- Rome III questionnaires
- Survival at the end of study period

Sample size

- Separately justified for each hypothesis
- Specification of primary outcome measure for hypothesis
- Type I error ≤ 0.05 and power ≥ 0.80
- Specification of primary comparison groups
- Specification of minimum clinically meaningful effect size for the primary outcome
- Specification of method for handling missing data
- No adjustments for multiplicity of comparisons

1. Background and rationale

1.1. Historical background

Gastroparesis is a devastating disease affecting predominantly young women (females outnumber males by a ratio of 4:1, with an average 34 years of age).¹ The symptomatic profile of gastroparesis includes nausea (90% of patients), vomiting (>80%), pain (~50%), early satiety (60%) and bloating (75%) and can vary in both the combination of symptoms and their severity.¹ Because of its chronic, and often intractable nature, the disorder has a tremendous impact on both patients and society at large. Gastroparesis remains difficult to treat, in large part because of the lack of knowledge of the underlying pathophysiology of this disease. Several factors, in particular, have impeded the progress in this field including the paucity of patients seen by any one center, the absence of uniform diagnostic criteria, the lack of generally available, reliable methods for physiological testing and the inaccessibility of tissue for histopathological correlation. Given the complexity of the problem, and the profound degree of morbidity currently associated with this disorder, a compelling need exists to study patients in a systematic, concerted manner. Such studies can best be achieved by recruiting patients and collecting data from multiple centers as part of a large network of investigators focused on this disorder. In recognition of this fact, the National Institute of Diabetes and Digestive and Kidney Diseases (NIDDK), through the mechanism of RFA-DK-05-004, established the Gastroparesis Clinical Research Consortium in 2006.

1.2. Gastroparesis Clinical Research Consortium

The Gastroparesis Clinical Research Consortium (GpCRC) is a cooperative network of six clinical centers, one satellite center, and one Data Coordinating Center (DCC). Clinical centers are responsible for proposing protocols, participating in their overall development, recruiting patients, conducting the research, and disseminating research findings. The individual clinical centers participate in a cooperative and interactive manner with one another and with the DCC in all aspects of the GpCRC. The DCC supports protocol development; provides sample size calculations, statistical expertise, forms, and data analysis; supports manuscript preparation; and provides overall study coordination and quality assurance, including coordination of the activities of the DCC also collaborates with the NIDDK Biosample (plasma, serum) and Genetics (DNA) Repositories for specimen banking.

A Steering Committee composed of the principal investigators of each clinical center in the Network, the principal investigator of the DCC, and the NIDDK Project Scientist represents the main governing body of the GpCRC. The Steering Committee has primary responsibility for the general organization of the GpCRC and for facilitating the development of a standardized nomenclature, diagnostic criteria, and the necessary components of the study database of patients with gastroparesis. The Steering Committee is also responsible for finalizing study protocols, supervising subject recruitment, monitoring study conduct, and reporting study results.

1.3. Mission of the GpCRC and overall objectives

The **mission of the GpCRC** is to improve our understanding of the pathogenesis and natural history of gastroparesis of all etiologies and to advance the diagnosis and therapy of patients affected with this troubling condition. The **overall objectives of the GpCRC** are to conduct multicenter, observational studies, and to conduct controlled treatment trials on well-characterized patients with gastroparesis.

1.4. Gastroparesis Registry

In order to achieve part of the overall objectives of the GpCRC, the GpCRC will construct and implement the **Gastroparesis Registry** (**GpR**) as an observational study to clarify the epidemiology, natural history, clinical course, and other outcomes of gastroparesis. The Gastroparesis Registry will consist of patients that meet specific criteria of gastroparesis that are recruited at the six clinical centers and satellite centers of the GpCRC. The Gastroparesis Registry will be used to collect data on patients with gastroparesis for the study of the epidemiology, etiology, and impact of gastroparesis. The patients in the Gastroparesis Registry will be a well-characterized cohort that will be followed to examine the natural history and clinical course of gastroparesis. Patients enrolled in the Gastroparesis Registry will be evaluated and treated according to the standards of care for this disorder, which has been formulated by the American Gastroenterological Association and the American Motility Society. The Gastroparesis Registry standards of care have been outlined by the GpCRC investigators and will be implemented through the study Standard Operating Procedures (SOPs). The Gastroparesis Registry will also serve as a means to readily identify well-characterized patients for enrollment in subsequent clinical and translational research studies. Fasting plasma, serum, and DNA samples will be collected and stored for ancillary studies of etiology and pathogenesis of gastroparesis.

2. Objectives and hypotheses

The specific objectives of the Gastroparesis Registry (GpR) are:

- To establish a registry of patients with gastroparesis for the study of the epidemiology, etiology, and degree of morbidity associated with gastroparesis.
- To prospectively and systematically follow a well-characterized cohort to define the natural history and clinical course of gastroparesis.
- To provide a reliable resource for rapid recruitment of well-characterized patients with gastroparesis for therapeutic clinical trials, pathophysiological, molecular, histopathologic, or other ancillary studies. These subsequent clinical trials or other ancillary studies will each be conducted under separate study protocols with separate consent processes.

Detailed epidemiological, clinical, physiological and patient outcome data will be collected in the GpR, with the long-term goal of phenotyping patients to classify them into pathophysiologically defined subsets. This classification will facilitate the search for etiopathogenesis such as genomic analysis and examination of viral "signatures", and will enhance the ability to define and conduct large clinical trials, ultimately leading to the development of more rational and effective therapeutic approaches for gastroparesis. In addition to these major clinical advances, the phenotypic classifications will also provide a strong foundation for experimental research and the development of relevant animal models.

2.1. Hypotheses to be tested

The major broad hypotheses that will be tested using the GpR as a primary tool are as follows:

- A grading system (mild, compensated, chronic failure) for gastroparesis can be developed that predicts the subsequent clinical course of patients.
- Most patients with gastroparesis have a disease course with episodes of exacerbations.
- The delay in gastric emptying predicts the clinical course of patients with gastroparesis.
- Delayed gastric emptying is linked to greater impairment in quality of life, increased economic cost, increased healthcare utilization, and worse clinical outcomes.
- Profound delays in solid food gastric emptying (e.g. less than 10% emptied at 2 hours or less than 25% emptied at 4 hours) relate to symptoms, whereas mild delays (e.g. 25- 50% emptied at 2 hours or 50-90% emptied at 4 hours) have no correlation with symptoms.
- Markedly accelerated early emptying (more than 75% emptied at 1 hour) relates to symptoms, whereas mildly accelerated emptying (50-75% emptied at 1 hour) has no correlation with symptoms.
- Weight loss in gastroparesis correlates with reduced fasting ghrelin levels.

Confidential, not for citation or attribution

5

- The clinical course of gastroparesis will vary by diagnostic categories such as diabetic, idiopathic, and post-surgical: (1) Diabetic gastroparesis will be related to the clinical course of a patient's diabetes mellitus and autonomic nervous system (ANS) neuropathy; (2) Post-infectious idiopathic gastroparesis will be different from other types of idiopathic gastroparesis.
- The survival outcomes of gastroparesis will vary by diagnostic categories such as diabetic, idiopathic, and post-surgical: Diabetic gastroparesis patients may have a shorter survival compared to other diagnostic categories.
- Symptom progression in diabetic gastroparesis relates to worsening autonomic dysfunction, dysrhythmias, fundic relaxation impairment, and visceral hyperalgesia.
- Control of gastropathy symptoms in diabetes (as opposed to improved emptying) leads to better glycemic control (decreased hemoglobin A1c).
- Patients with type 1 diabetes mellitus and type 2 diabetes mellitus with HbA1c greater than 8.5%, 7.5 to 8.5% and 6.5 to 7.5% will have different upper GI symptoms, different gastric dysrhythmias and different rates of gastric emptying.
- The clinical course of idiopathic gastroparesis patients with positive autoimmune markers will differ from patients without the autoimmune markers.
- Symptom resolution in postviral gastroparesis relates to improved gastric emptying, gastric dysrhythmias, fundic accommodation, visceral hyperalgesia.
- Symptoms in postfundoplication gastroparesis show improvement over the first 2 post-operative years that does not relate to improved vagal function (i.e. non-vagal pathways are recruited).
- Severe abdominal pain is infrequently the predominant symptom in patients with gastroparesis.
- Lifetime stressful events and a history of abuse relate to symptom severity in gastroparesis.
- Symptoms of gastroparesis fluctuate over time and worsen in the last half of the menstrual cycle.
- A subset of patients with gastroparesis have evidence of an inflammatory process. These patients have a slow downhill course.
- Nausea, but not vomiting or abdominal pain, is associated with the decreased quality of life in patients with gastroparesis.
- Specific genetic markers can be identified in patients with familial forms of gastroparesis.
- A heritable component of gastroparesis is detectable in patients with type 2 diabetes mellitus.
- Associated phenomena such as autonomic neuropathy or dysmotility of other gastrointestinal regions are important in determining the natural history and clinical outcomes in patients with gastroparesis.
- A subset of patients with gastroparesis will also have subtle or overt dysmotility of the small and/or large intestine which will adversely impact prognosis.
- Patients with type 2 diabetes mellitus have high prevalence of upper GI symptoms, gastric dysrhythmias, and gastroparesis (comparable to literature for patients with type 1 diabetes mellitus).

3. Scientific background

Gastroparesis is a disorder of gastric neuromuscular sensory and motor function that affects patients (most of whom are women) in the prime of their life. Inadequate understanding about the pathogenesis of this condition, coupled with a general lack of awareness of the disease amongst most clinicians has led to a haphazard and often ineffective approach to treatment. The traditional concept of gastroparesis being defined as a disorder of delayed gastric emptying has dominated physician thinking for decades and has influenced the management approaches to these patients. However, as discussed below, the relationship between gastric emptying and symptoms is a very loose one and a rigid adherence to this definition may result in the dismissal of many patients with genuine illness. Second, prokinetic agents are frequently ineffective as sole therapeutic agents. Third, preoccupation with gastric emptying has distracted attention from symptoms such as nausea and pain, and diverted resources that could have led to the development of effective therapies for them. On the other hand, documentation of delays in gastric emptying may be useful to distinguish patients with gastroparesis from individuals with normal emptying rates who have similar symptoms and might be considered to have functional dyspepsia or functional vomiting. It is likely that there is significant overlap not only symptomatically, but also in terms of underlying pathophysiological changes in gastric function in the different clinical conditions.²

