3.2. Epidemiology and natural history

The prevalence of gastroparesis is not known; however, it has been estimated that up to 4% of the population experiences symptomatic manifestations of this condition.⁴ Diabetes mellitus is the most common systemic disease associated with gastroparesis. A similar number of patients present with gastroparesis of an idiopathic nature. Postsurgical gastroparesis, often with vagotomy or damage to the vagus nerve, represents the third most common etiology of gastroparesis. Published data from specialized centers suggest that gastroparesis can develop in 20-55% of patients with type 1 diabetes and up to 30% of patients with type 2 diabetes, however the incidence and prevalence may be lower in the general community of diabetics who do not seek specialized care.^{5,6} Furthermore, gastroparesis is seen in up to 34% of patients with functional dyspepsia, although the degree of gastroparesis is usually milder than that seen in diabetics.⁷

The majority of gastroparetics, whether of the diabetic or idiopathic type, are women (up to 80% in some series). Patients are typically young to middle aged. The natural history of gastroparesis is poorly understood and, even in diabetics, symptoms may fluctuate considerably with many patients reporting relatively symptom-free intervals of varying durations. In others, a progressively downhill course is observed requiring interventional procedures to restore nutritional intake and provide palliation. A subset of the idiopathic variety may present with abrupt onset of symptoms, sometimes

PCS=physical component summary; MCS=mental component summary

in association with acute gastroenteritis or other non-specific illness, and it is presumed that this may represent a post-viral syndrome. The prognosis in such cases has been reported to be better than other subtypes with gradual return to normal over several years in a significant proportion of patients.⁹

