4.4. Target composition

It is expected that 80% of patients will meet the definition of gastroparesis as above with delayed gastric emptying. We will cap the number of the patients with symptomatic nausea and vomiting without delayed gastric emptying (as described in section 4.3 above) to 20%. Patients will be recruited predominantly from outpatient clinics either in gastroenterology, diabetes or primary care settings. Inpatients with the diagnosis of gastroparesis may also be invited to participate once they are discharged from the hospital and more stable medically.

Gastroparesis Registry Protocol

5. Screening and enrollment

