5.1. Inclusion criteria

- Symptoms of gastroparesis of at least 12 weeks duration (do not have to be contiguous) with varying degrees of nausea, vomiting, abdominal pain, early satiety, post-prandial fullness,
- Completion of a 4-hour scintigraphic low fat Egg Beaters gastric emptying study
 - Patients with either or both abnormal 2 hour (>60% retention) and 4 hour (>10% retention) gastric emptying will be enrolled and classified as definite gastroparesis (Gp)
 - Patients with normal gastric emptying, but with symptoms of gastroparesis may be enrolled and classified as possible gastroparesis or gastroparesis-like with normal gastric emptying (GLNGE)
- Age at least 18 years at initial screening visit
- Ability and willingness to participate in follow-up

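### The Registry cannot test the hypothesis of a high prevalence of symptoms, dysrhythmias and gastroparesis in type 2 diabetes, because entry is conditional on symptoms

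*Protocol*

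**What the plan says.** Section 2.1 of the protocol introduces its list with "The major broad hypotheses that will be tested using the GpR as a primary tool are as follows". The last of the 25 bullets is that "Patients with type 2 diabetes mellitus have high prevalence of upper GI symptoms, gastric dysrhythmias, and gastroparesis", with the type 1 literature named as the yardstick.

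The entry rules are in Sections 4 to 6. Section 5.1 requires "Symptoms of gastroparesis of at least 12 weeks duration (do not have to be contiguous"), and patients with normal emptying also enter only if they have symptoms. The overview in Section 6 says that patients come largely from the investigators' own rosters and from referrals for gastroparesis. They proceed to formal screening only if judged to have definite or possible disease. Section 4.4 adds: "It is expected that 80% of patients will meet the definition of gastroparesis as above with delayed gastric emptying". It caps symptomatic patients without delayed emptying at 20%.

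The literature figures are in Section 3.2, which reports from specialized centers that "gastroparesis can develop in 20-55% of patients with type 1 diabetes and up to 30% of patients with type 2 diabetes" and warns that the figures may be lower among diabetics in the general community.

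Section 7 exempts the Section 2.1 hypotheses from multiplicity adjustment. Only hypotheses outside that list must be labelled exploratory.

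**The concern.** The bullet is about a proportion among people with type 2 diabetes. The Registry observes only those people with type 2 diabetes who already have the symptoms and are suspected of having the disease. Two of the three quantities in the bullet (symptoms and gastroparesis) are thus conditioned on at entry, wholly or in part. The third (dysrhythmia) has no scheduled measurement.

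What is at stake is the standing of a published result. A percentage produced by the entry criteria could be reported as the answer to a pre-specified hypothesis, without the exploratory label, beside literature figures that have a different denominator. No analysis plan or later publication proposal can repair this. Section 7 lets a proposal choose a subgroup of Registry patients, but no subgroup of a symptom-selected cohort contains the missing patients without symptoms.

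**Working it through.** The protocol gives no sample size, power or precision for this hypothesis, so there is no stated figure to reproduce. The check takes each component of the bullet in turn.

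**1. Symptoms.** Every enrolled patient has gastroparesis symptoms (Section 5.1). With n enrolled type 2 patients, the share with any symptoms is n/n = 100%, whatever the prevalence in type 2 diabetes. The frequency of each individual symptom is not fixed in this way.

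**2. Gastroparesis, symptom criterion alone.** Let p be the true prevalence of delayed emptying in type 2 diabetes, a the probability of symptoms given delayed emptying, and b the probability of symptoms without it. Among symptomatic patients the share with delayed emptying is

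s = p·a / (p·a + (1 − p)·b).

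The protocol gives neither a nor b, so three assumed pairs are shown. For example, p = 0.20, a = 0.9, b = 0.1 gives 0.18 / (0.18 + 0.08) = 69.2%.

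| True p | a = 0.9, b = 0.1 | a = 0.9, b = 0.3 | a = 0.5, b = 0.5 |
|---|---|---|---|
| 5% | 32.1% | 13.6% | 5.0% |
| 10% | 50.0% | 25.0% | 10.0% |
| 20% | 69.2% | 42.9% | 20.0% |
| 30% | 79.4% | 56.3% | 30.0% |

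The same prevalence of 20% yields anything from 20.0% to 69.2%. Prevalences of 5% and 30% can yield 32.1% and 30.0%. The share does not identify p unless a and b are known, and the Registry cannot estimate them because it enrols nobody without symptoms. Referral adds a further, unmodelled selection.

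**3. Gastroparesis, effect of the cap.** At the full 700 patients (Section 7), the cap allows 0.20 × 700 = 140 patients without delayed emptying, which leaves at least 560 (80%) with it. If the cap acted in proportion within type 2 diabetes, every entry in the table would be raised to 80%, since the largest is 79.4%. But Section 4.4 applies the cap to the whole Registry. With n₂ type 2 patients, the smallest delayed share that the cap permits among them is 1 − min(1, 140/n₂):

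| Type 2 share of Registry (assumed) | n₂ | Smallest delayed share |
|---|---|---|
| 10% | 70 | 0% |
| 20% | 140 | 0% |
| 30% | 210 | 1 − 140/210 = 33% |
| 50% | 350 | 1 − 140/350 = 60% |

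The cap can distort the type 2 share but does not fix it. The conclusion in step 2 does not need it.

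**4. Comparator.** The 20-55% in Section 3.2 is a share of type 1 diabetics seen at specialized centers. The Registry figure would be a share of symptomatic patients suspected of gastroparesis. These are proportions of different populations, and agreement or disagreement between them says nothing about the hypothesis.

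**5. Dysrhythmia.** The schedule in 10.2 has no electrogastrography row, and Section 6.2 only records additional GI tests done as standard of care. Dysrhythmia would be known only for patients whom someone chose to test.

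**The case against.** The strongest defence is procedural. Section 7 calls the hypotheses intentionally broad, and each needs a proposal with comparison groups, subgroup definition, methods and sample size, approved by the Steering Committee and reviewed by the DSMB. Section 2.1 calls the Registry a primary tool, not the only one, and ancillary studies run under separate protocols. The point also concerns one of 25 hypotheses and touches no patient risk or enrolment rule. All this bears on how serious the flaw is. It does not supply a denominator, and the bullet still assigns the test to the Registry.

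Three stronger readings are tempting, and the documents do not support them.

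- *That gastroparesis would appear in about 80% of type 2 patients because of the cap.* The cap and the 80% expectation are Registry-wide (step 3).
- *That the hypothesis would be confirmed whatever the truth.* Dysrhythmia is not an entry criterion, so that component is not fixed by inclusion. The bullet also predicts a level comparable to the type 1 literature, and a figure of 80% would not be comparable with 20-55%. The figure of up to 30% for type 2 is not the bullet's comparator.
- *That the hypothesis "A heritable component of gastroparesis is detectable in patients with type 2 diabetes mellitus" fails for the same reason.* Detecting a heritable component does not require a prevalence denominator. Family history is captured (Section 6.3), DNA is banked (Section 6.4), and nothing bars symptomatic type 2 patients with normal emptying from enrolling. The absence of asymptomatic controls limits some designs but is no ground for deleting the bullet.

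**Conclusion.** The concern holds for the prevalence bullet. As written, the hypothesis is not testable in this cohort. The share with any symptoms is 100% by entry, the share with delayed emptying does not identify the prevalence, and dysrhythmia is not systematically measured.

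The symptom criterion in Section 5.1 and the screening rule in Section 6 are enough to establish this. The table in step 2 rests on assumed symptom probabilities and only illustrates how far the enrolled share can depart from the true prevalence. The cap is a secondary, Registry-level influence. The problem is selection, not error rate, so a multiplicity adjustment would not help. The size of the bias cannot be stated from the documents, because they give neither the symptom probabilities nor the expected number of type 2 patients.

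**What to change.** In Section 2.1, either delete the prevalence bullet or restate it as a comparison of enrolled type 1 and type 2 patients on PAGI-SYM scores and baseline gastric retention. The second option should be aligned with the existing bullet on type 1 and type 2 patients by HbA1c band, which already covers symptoms and emptying rates, so that the two do not duplicate each other. The restated bullet should describe enrolled patients only and leave out dysrhythmia, which the schedule does not measure.

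In Section 7, add a sentence that the Registry does not estimate the prevalence of symptoms or gastroparesis in diabetes, because entry is conditional on symptoms. The heritability bullet can stay.

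The cost is wording. Diabetes type, PAGI-SYM and scintigraphy are already collected at baseline, so no data item, visit or patient is added. One hypothesis is withdrawn or narrowed.

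### The Registry cannot test the Section 2.1 hypothesis about prevalence in type 2 diabetes, because it has no sample of type 2 diabetics unselected for symptoms

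*Protocol*

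**What the plan says.** Section 2.1 introduces its list with: "The major broad hypotheses that will be tested using the GpR as a primary tool are as follows". The last of the 25 bullets reads: "Patients with type 2 diabetes mellitus have high prevalence of upper GI symptoms, gastric dysrhythmias, and gastroparesis", followed by a parenthesis giving the benchmark: "comparable to literature for patients with type 1 diabetes mellitus".

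Four other places decide who can contribute to that hypothesis:

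- Section 5.1 requires of every patient: "Symptoms of gastroparesis of at least 12 weeks duration (do not have to be contiguous) with varying degrees of nausea, vomiting, abdominal pain". On emptying it says: "Patients with either or both abnormal 2 hour (>60% retention) and 4 hour (>10% retention) gastric emptying will be enrolled and classified as definite gastroparesis". Those whose emptying is normal may enter, but only if they have symptoms of gastroparesis.
- Section 4.4 says: "It is expected that 80% of patients will meet the definition of gastroparesis as above with delayed gastric emptying". It caps the symptomatic group with normal emptying at 20% of the cohort.
- Section 6 (overview) admits to formal screening only patients already considered to have definite or possible gastroparesis.
- Section 7 says that nearly all questions will be answered in subgroups of Registry patients. It waives multiplicity adjustment for the Section 2.1 hypotheses and keeps the exploratory label for hypotheses that were not pre-specified.

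The literature figures are in Section 3.2: "gastroparesis can develop in 20-55% of patients with type 1 diabetes and up to 30% of patients with type 2 diabetes". The same sentence warns that the frequency may be lower among diabetics who do not seek specialised care.

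**The concern.** A prevalence is a fraction of a population. To estimate it in type 2 diabetes, one needs type 2 diabetics who were not chosen for having the condition being counted. The Registry enrols patients because they have symptoms, and most of them because they also have delayed emptying. Type 2 diabetics without symptoms, who belong in the denominator, cannot enter.

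At stake is a result that eligibility and recruitment largely produce but that Section 7 would let the consortium report as pre-specified and not exploratory. A later analysis plan cannot repair this, because what is missing is the denominator and not a method. The publication proposals required by Section 7 define subgroups of Registry patients, and no such subgroup contains the people who are absent.

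**Working it through.** The protocol gives no sample size, power or target prevalence for this bullet, so there is no stated figure to reproduce. The three parts of the hypothesis are checked in turn.

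**1. Upper GI symptoms.** Entry requires qualifying symptoms of every patient, so the share of enrolled type 2 patients with any such symptom is n/n = 100%, whatever the frequency among type 2 diabetics at large. The frequency of each single symptom is not fixed by this rule.

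**2. Gastric dysrhythmias.** These are not an entry criterion, so the rules do not set their frequency. They would still be seen only in symptomatic, selected patients. The data collection schedule (Section 10.2) lists no electrogastrography. Section 6.2 records additional GI tests done as standard of care, so recordings would come only from patients who were tested clinically.

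**3. Gastroparesis.** Inputs: up to 700 patients (Section 7), 80% expected with delayed emptying and a 20% cap (Section 4.4), literature 20-55% for type 1 and up to 30% for type 2 (Section 3.2). The cohort split is 0.80 × 700 = 560 delayed and at most 0.20 × 700 = 140 normal.

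*Does the Registry share follow the true prevalence?* Let π be the proportion of type 2 diabetics with symptomatic delayed emptying, and s the proportion of the rest who have symptoms with normal emptying. Among symptomatic patients the natural delayed share is π / [π + (1 − π)s]. If the 20% cap acts on type 2 patients as on the cohort (assumption), the Registry share is the larger of 0.80 and that value. The values of π and s are assumed.

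| π | s | Natural share among symptomatic | Registry share |
|---|---|---|---|
| 0.01 | 0.10 | 0.092 | 0.80 |
| 0.05 | 0.10 | 0.345 | 0.80 |
| 0.10 | 0.30 | 0.270 | 0.80 |
| 0.30 | 0.10 | 0.811 | 0.811 |
| 0.30 | 0.30 | 0.588 | 0.80 |

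A thirtyfold change in π, from 1% to 30%, leaves the Registry share at 80-81%.

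*How would this compare with the literature range?* Assume a delayed share of 80% in the type 2 subgroup and an exact one-sided binomial test at 0.025. The protocol does not give the number of type 2 patients, so n is varied. The critical count r is the smallest with P(X ≥ r | n, p0) ≤ 0.025. The table gives P(X ≥ r | n, 0.80).

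| n | r for p0 = 0.30 | Chance of showing >30% | r for p0 = 0.55 | Chance of showing >55% |
|---|---|---|---|---|
| 30 | 15 | 0.9999 | 23 | 0.76 |
| 50 | 23 | >0.9999 | 35 | 0.97 |
| 100 | 40 | >0.9999 | 66 | 0.9997 |
| 150 | 57 | >0.9999 | 95 | >0.9999 |

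If exactly 80% were observed, the Clopper-Pearson 95% intervals would be 56-94% (16/20), 66-90% (40/50) and 71-87% (80/100).

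*Is the type 2 share fixed by rule?* No. The cap covers the whole cohort. With 210 type 2 patients (30% of 700, assumed) and all 140 normal-emptying patients among them, the share would be (210 − 140)/210 = 33%. With none among them it would be 100%. Either way, the figure describes who was recruited.

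**The case against.** A reader might infer that the entry rules alone confirm the hypothesis. The documents do not support that reading, for four reasons.

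- The bullet claims a level comparable to the type 1 literature. A share near 80% would lie above 20-55%, so it would contradict that part. The 20-55% concerns gastroparesis only, and Section 3.2 gives no type 1 figure for overall upper GI symptoms or for dysrhythmias.
- Dysrhythmia is not an entry criterion.
- The 80% is an expectation and the cap is cohort-wide. The 33% case above is extreme, but it falls inside the literature range.
- The intervals rest on assumed numbers of type 2 patients and an assumed observed 80%. With a true share of 80% and n = 20, the chance of 16 or more is about 63%, and 15/20 would give a lower limit near 51%, below 55%.

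It can also be said that the Registry is called a primary tool, so another source is not excluded. Section 7 also requires a proposal for each hypothesis, with comparison groups and a sample size justification, Steering Committee approval and review by the DSMB. Finally, this is one of 25 deliberately broad hypotheses in an observational study, and symptom-by-symptom frequencies within the cohort are informative.

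These points limit the wording and the weight of the finding. They do not supply a denominator. No other data source is described, the proposal process works with subgroups of Registry patients, and a within-cohort frequency is not a prevalence in type 2 diabetes.

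**Conclusion.** The point holds in this form: neither the high nor the comparable part of the bullet can be validly tested in the Registry. The any-symptom part is fixed at 100% by entry. The gastroparesis part reflects case selection and recruitment mix. It is about 80% if type 2 patients follow the cohort target, and then it tends to exceed the cited range whatever the true prevalence. That tendency rests on two assumptions, the 80:20 mix within type 2 patients and the subgroup sizes used above. The dysrhythmia part is not settled by entry, but it has no unselected sample and no scheduled measurement.

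The conclusion itself does not need those assumptions. It follows from the symptom requirement and from the different denominator of the literature figures. The stronger claim, that eligibility proves the hypothesis, should not be made.

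The damage is confined to one bullet. The cohort, its follow-up and the other hypotheses are unaffected.

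**What to change.** Delete the bullet from Section 2.1. Alternatively, restate it as a comparison, among enrolled diabetic patients, of type 2 with type 1 on PAGI-SYM scores and on 2-hour and 4-hour retention. Section 2.1 already has a hypothesis on type 1 and type 2 patients by HbA1c band that covers upper GI symptoms, dysrhythmias and emptying rates, so the restated bullet should be merged with it. The text should note that both groups are selected on symptoms, which limits what a difference between them, or its absence, can mean.

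Add one sentence saying that the Registry will not be used to estimate the prevalence of symptoms or gastroparesis in the diabetic population. Keep it that narrow: within-cohort frequencies may still be reported, and other bullets need them, such as the one on severe abdominal pain as the predominant symptom.

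The cost is a small text change. Diabetes type (Section 6.3), PAGI-SYM and baseline scintigraphy (Section 10.2) are already collected. The sponsor gives up a population-prevalence claim that the design cannot support. Answering that question would take a separate study that samples type 2 diabetics regardless of symptoms.
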